A randomised assessor-blinded comparison of low irradiance and conventional irradiance photodynamic therapy for superficial non-melanoma skin cancer

Protocol

Chief Investigator:

Investigators:

Introduction

Skin cancer is the commonest malignancy in Caucasians and is a major cause of morbidity and burden on health services¹. Patients with superficial non-melanoma skin cancer (NMSC) are frequently elderly and frail and surgery is often not appropriate or feasible and non-surgical approaches, such as topical photodynamic therapy (PDT), are ideally suited to treat these lesions. Topical PDT has been increasingly used to non-invasively treat superficial NMSC and dysplasia since its introduction in 1990 and this now has National and European Guidelines for use and NICE technology (<http://guidance.nice.org.uk/IPG155>) and Scottish Medicines Consortium approval (Methyl aminolevulinic acid (Metvix cream) - SMC approval for AK (50/03) and BCC (51/03) November 2003 <http://www.scottishmedicines.org.uk>)²⁻⁴.

At present PDT is hospital-based and requires the patient to come up as a day case, wait for 3 - 6 hours (depending on the treatment regime), while the cream is in place and conversion to the photosensitiser occurs, before irradiation takes place over a further 15 - 20 minutes. Essentially, patients are at the hospital for most of the day. Treatment is repeated at one week, and these two treatments one week apart constitute a treatment cycle.

Subsequently, at three month follow-up, if complete resolution of the lesion is not apparent then a second treatment cycle is undertaken. Thus, this will require the patient to attend for four day case procedures, which is tiring and time consuming for elderly, frail patients and, because of the time involved, limits the number of patients that can be treated in one session at the hospital. Thus, there is a major demand for treatment to be more efficient and patient-orientated.

Furthermore, during the irradiation of PDT significant pain is experienced by most patients. In our Unit, 16% of PDT treatments (n=4717) were associated with severe pain. The mechanism of PDT-induced pain is not well understood and conventional methods of pain relief, such as topical anaesthetics are not very effective⁵⁻⁷. This can limit successful delivery of PDT and negatively impact on the patient's experience of treatment.

Low irradiance irradiation enhances photobleaching efficiency and the PDT effect when compared with higher irradiance light delivery, as oxygen depletion is less rapid when irradiation occurs over a longer time period⁸, reviewed in ⁹). Furthermore, there is preliminary evidence that low irradiance PDT is less painful than conventional PDT, and indeed if this is the case, then this would significantly improve the patient's experience of PDT and successful delivery and wide acceptance of this therapy^{10,11}. We will translate these findings into clinical practice by investigating low irradiance ambulatory PDT in the proposed clinical trial.

Results of pilot studies

A novel CE-marked portable red light LED source has been developed in the form of a "skin cancer plaster" (Ambulight, Ambicare Health). This is able to deliver a standard PDT light dose at very low irradiance over a prolonged time period. Thus, the Ambulight delivers light at low irradiance (7 mW/cm² as compared to 80-90 mW/cm² with conventional PDT), such that the total dose (75 J/cm²) is delivered over 3 hours as compared to approximately 15 - 20 minutes for conventional hospital-based devices. The light source is small, light and compact and attached to a battery pack, such that patients can put the battery pack in a pocket and be mobile during treatment. This has been established in clinical practice in order for patients to receive treatment at home.

Initial studies of prototype devices in small numbers of patients showed that it could be successfully used for low irradiance topical PDT, and preliminary data suggested that treatment was less painful and of similar efficacy to conventional PDT^{9,12}. Subsequently, the more portable and compact Ambulight device was developed and our preliminary clinical data using this in eight patients with multiple lesions of NMSC who were treated simultaneously with both conventional PDT and low irradiance Ambulight PDT showed a significant difference in pain experienced, with the VAS score for pain of conventional PDT being 5.2 (2 - 9) cm compared with 1.5 (0 - 3) cm for low irradiance Ambulight PDT (values given as median (range), p<0.05).

Study aims

The primary aim of this study is to examine whether the pain and discomfort of topical PDT is significantly different when using the low irradiance ambulatory LED device compared with conventional higher irradiance PDT and this is the first randomised controlled trial in this important clinical area. We will also examine possible differences in phototoxicity of the two

regimes and assess patient evaluation of treatment. The secondary end-point of efficacy of the two treatment regimes will be examined.

Research Questions

1. Is there a significant difference in pain and phototoxicity experienced with low irradiance ambulatory PDT compared with conventional higher irradiance PDT?
2. Is there a large difference in efficacy of treatments at one year follow-up?
3. Do patients prefer ambulatory or conventional PDT?

Clinical trial study design

a prospective, randomised, controlled, single-blind, comparison of low irradiance ambulatory MAL-PDT with conventional higher irradiance MAL PDT for patients with superficial NMSC.

Participants

Study details would be disseminated to local dermatology colleagues and plastic surgeons, as these are the sources of referral to the PDT Clinic in the Photobiology Unit. The PI will screen all referral letters for PDT and any patient with superficial basal cell carcinoma or Bowen's disease (diameter \leq 2 cm) will be sent out a Participant Information Sheet (PIS). They will be invited to participate in the study when they attend the PDT clinic. Exclusion criteria will be patients with lesions $>$ 2 cm diameter, patients unable to give consent, patients with lesions at sites where the portable device would be difficult to apply such as highly curved sites e.g. rim of ear. The aim will be to recruit 50 patients and they will be randomised to receive either low irradiance ambulatory PDT or conventional higher irradiance PDT. After obtaining written consent, demographic details and assessment of the lesion will be undertaken and the area will be mapped and photographed.

Randomisation

A blocked randomisation list will be computer generated. Randomisation codes will be concealed in opaque sealed envelopes and will only be opened at the time of entry of the patient to the study and this will be carried out by the Photobiology Technician. Patients will then receive their randomised treatment and this will also be undertaken by the Photobiology Technician as is the normal clinical practice in the PDT Unit.

Interventions

The study outline is shown in **Appendix 1**.

Treatment allocations will be:

Conventional PDT: Lesions will be gently scraped using a disposable ring curette (Stiefel®) and MAL cream (16% w/v, Galdema UK) will be applied to the lesion and occluded under Tegaderm® and Mepore® for three hours. Dressings and residual cream will then be carefully removed and irradiation of the lesion, including a 5 mm rim of clinically normal-appearing tissue, will be undertaken. Irradiation will be performed using the Aktilite 128/16 device (peak wavelength 636 nm, full width half maximum (FWHM) 18 nm) to deliver a total dose of 75 J/cm². Immediately after irradiation a dressing will be applied and the patient will go home.

Low irradiance ambulatory PDT: The lesion will be prepared and MAL cream applied as above. Immediately after cream application, the Ambulight device will be applied and will adhere to the

treatment site. This is automated to be in place and switched off for three hours and will then switch on and irradiate the lesion for a further three hours to deliver a total dose of 75 J/cm² (peak wavelength 640 nm, FWHM 25 nm). The Ambulight device has a green light displayed when device is active. A red light will be displayed if the device is not working properly. The green light will go off at the end of the planned automated treatment time. The patient will be free to go home once the cream and device are in place and will be advised about how to remove the plaster at the end of the irradiation period. The battery pack and used adhesive plaster are put in bags and then in the pre-paid envelope (supplied by the treatment centre) and posted back to the Photobiology Unit where the battery pack will be cleaned, recharged and re-calibrated and the dressing head sent back to the manufacturer for recycling.

Assessments (Appendix 1 and 2)

Re-treatment and assessment: Seven days later the patient will return for the second treatment, which will be repeated as per the first week and the treatment allocation. Prior to the second treatment, patients will be asked to complete a VAS score of 0 - 10 cm for the maximal recall of pain and discomfort experienced during the first PDT treatment. Additionally, the phototoxic reaction of the first treatment will also be assessed on a semi-quantitative scale for erythema (0-3), oedema (0-1), blistering (0-1), crusting (0-1) and ulceration (0-1) at this time point. This second treatment then completes the first treatment cycle.

Follow-up assessment at one week: The patient will return one week later and, again, pain and phototoxicity will be assessed as above.

Follow-up assessment at three months: Patients will be reviewed at three months and a clinical assessment of whether there is clearance (defined as absence of residual surface change, scale, infiltration or significant erythema) (CR), partial response (presence of residual surface change, scale, infiltration or prominent erythema) (PR) or no response (no change from baseline appearance) (NR) will be made. For patients with PR or NR a second treatment cycle will be performed according to the original randomisation. Again, pain recall and phototoxicity will be assessed one week after each of these treatments as per the first treatment cycle.

Follow-up assessment at six months: All patients will receive a follow-up assessment at 6 months. Those who do not exhibit a complete response on clinical assessment (after one or two treatment cycles) will receive an alternative treatment at the doctor's discretion and the patient will have completed the study. An overall assessment of the patient's evaluation of treatment will also be recorded in all patients's notes at this time point. This evaluation will take into account the patient's perception of efficacy, adverse effects and convenience of treatment and their overall satisfaction with the PDT regime they received.

Follow-up assessment at 12 months: All patients remaining in the study (i.e. those with CR at 3 months and/or 6 months) will undergo final clinical assessment of efficacy of treatment (clear or not clear) at 12 months after the first PDT treatment cycle. Histological analysis will not be undertaken as part of the study as these patients will usually have been selected for PDT on the basis that surgery was not considered appropriate.

Data processing and statistical analysis

Statistical power: From our original published data with the prototype device, the mean pain score of patients treated with ambulatory low irradiance PDT (n=12) was 1.25 (standard deviation 0.4) and was 5.26 (standard deviation 2.38) for a historical cohort of patients treated

with conventional PDT (n=50) (10). Based on this we estimated that to give 90% power to detect as significant at the 5% level ($p < 0.05$ as significant), a difference in mean pain score in one group of 2 compared with the mean pain score of 4 in the other group, assuming two-sided testing, a minimum of 36 subjects would be needed. Therefore, we plan to incorporate a safety margin recruiting 50 subjects given the old and frail nature of patients as this would account for any drop-outs. Over the last 2 years, we have treated 60 - 80 new patients per year with topical PDT. 82% of these were patients with Bowen's disease or superficial basal cell carcinoma and we estimate that of these at least 50% should fit the eligibility criteria for the study. Therefore, we estimate that recruitment will be finished within 2 years, and with a one year follow-up, the overall study will be completed within 3 years.

Blinding: Blinding of the patient and the Photobiology technician will not be possible. The study will remain blinded to the CI and co-investigators until database lock, after which the study statistician will be unblinded. Any necessary clinical communications will be carried out by a Photobiology Unit clinician unrelated to the study. These clinicians will be the photodermatology Specialist Registrars.

Data recording and analysis: Analyses will involve assessment of tabulated and graphical data and this will be followed by use of appropriate statistical tests comparing the pre-planned outcome measures. Analysis will be on an intention-to-treat basis, where possible. Reporting of study data will be based on CONSORT guidance.

Timetable of work

Patient recruitment will be completed by the end of year 2 and follow up by the end of year 3. Final analysis of outcome measures will be undertaken in year 3.

Key references

3. Braathen LR, Szeimies R-M, Basset-Sequin N et al. Guidelines on the use of photodynamic therapy for nonmelanoma skin cancer: an international consensus. *J Am Acad Dermatol* 2007; 56: 125-143

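### At the first treatment the technician prepares the lesion already knowing the arm, although scraping and cream are the same in both arms and could come before the envelope is opened

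*Combined protocol and SAP*

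**What the plan says.** Protocol, Randomisation: a computer-generated blocked list is concealed in sealed opaque envelopes. An envelope "will only be opened at the time of entry of the patient to the study", and "this will be carried out by the Photobiology Technician". The text continues: "Patients will then receive their randomised treatment and this will also be undertaken by the Photobiology Technician". The block size is not stated.

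Protocol, Interventions, conventional arm: the first step is that "Lesions will be gently scraped using a disposable ring curette", after which MAL cream is applied and occluded for three hours. Ambulatory arm: "The lesion will be prepared and MAL cream applied as above", and then "Immediately after cream application, the Ambulight device will be applied".

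Protocol, Blinding: "Blinding of the patient and the Photobiology technician will not be possible". No distinction is made between the shared preparation and the steps that differ by arm.

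Protocol, Participants: lesions at sites where the device would be hard to fit are excluded from the whole trial. After consent, the lesion is assessed, mapped and photographed.

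**The concern.** Scraping and cream application are done by hand, and the plan standardises the scraping only by naming the instrument and asking that it be gentle. If the operator knows the arm while doing them, any difference in how thoroughly the lesion is prepared becomes part of the comparison. No analysis could then separate it from the effect of the device.

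Pain is the primary aim, and it is scored from recall by patients who know their treatment. That route to bias cannot be closed, which is a reason to close another where it is cheap to do so. The unit also has pilot results favouring the device (median VAS 5.2 cm conventional against 1.5 cm ambulatory, Results of pilot studies), so staff may not be neutral in what they expect.

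**Working it through.** **1. Order of events at the first treatment**, from Participants, Randomisation and Interventions:

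| Step | Conventional | Ambulatory | Must the arm be known? |
|---|---|---|---|
| Consent, demographics, lesion assessment, mapping, photographs | same | same | No |
| Envelope opened | at entry | at entry | – |
| Scraping with ring curette | yes | yes, by cross-reference | No |
| MAL cream | yes | yes, by cross-reference | No |
| Covering | occlusive dressing | Ambulight device | Yes |
| Irradiation | Aktilite, after the dressing is removed | automated, in place | Yes |

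The envelope is opened two steps earlier than any step needs it. The statement that the technician cannot be blinded is right for the last two rows. It is not right for scraping and cream at the first treatment.

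**2. How much could be masked.** The second treatment (day 7) and any second cycle follow the original allocation, so the technician may already know the arm.
- First cycle: 1 of 2 treatments = 50%. With 50 patients, this is 50 of 2 × 50 = 100 planned first-cycle treatments.
- Patients with a second cycle: 1 of 4 treatments = 25%.

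The pain score for the first treatment is recorded separately, just before the second treatment, so the masked step relates to an identifiable score.

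**3. The plan's sample size.** Inputs from Statistical power: difference 4 − 2 = 2; SDs 0.4 and 2.38; two-sided 5%; 90% power; minimum 36 in total. The method is not stated. A Welch t-test with 18 per arm (equal allocation assumed) gives:
- SE = √((0.4² + 2.38²)/18) = √(5.8244/18) = 0.569
- non-centrality = 2/0.569 = 3.52, with about 18 degrees of freedom
- power = 91.3%, and 18 is the smallest number per arm that reaches 90%, so the total is 36.

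The stated figure is reproduced. Nothing in it depends on when the envelope is opened.

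**4. Scale, by assumption only.** The documents give no figure for a pain shift caused by preparation. Suppose a shift *b* of 0.25 to 0.5 cm between arms. Against the planned difference this is 0.25/2 = 12.5% to 0.5/2 = 25%. With no true difference, 25 per arm and an equal-variance t-test, non-centrality is *b*/(SD × √(2/25)). The SD is taken as 1.71 (root mean square of 0.4 and 2.38) or 2.38:

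| Assumed shift | SD 2.38 | SD 1.71 |
|---|---|---|
| 0.25 cm | 6.5% | 8.0% |
| 0.5 cm | 11.3% | 17.4% |

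The entries are two-sided type I error against the nominal 5%. They apply if the whole shift falls on the score that is analysed. If the two first-cycle scores were averaged and the shift occurred at both treatments, masking the first would remove only half of it, 0.125 to 0.25 cm. These are illustrations, not estimates.

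**The case against.** The strongest reply is that no harm is shown. No section links scraping or cream coverage to pain. The Introduction places the pain during irradiation and calls its mechanism poorly understood. No direction of bias can be derived from the documents. This stands: the mechanism is plausible but not documented, and the shifts in the working are assumed.

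Second, preparation is partly standardised (one instrument, one cream, a cross-reference between arms), and the plan openly accepts an unblinded operator. This also stands in part. It makes the point a design choice that could be improved, not an error or a contradiction.

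Third, the gain is partial. Later treatments stay unblinded, and the larger source of bias, recall by unblinded patients, is untouched. This stands in full.

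Fourth, that the technician does the scraping is inferred from the sentence about delivering the randomised treatment. It is an inference, but the natural one.

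A reader might also infer three stronger things that the documents do not support:
- **That allocation concealment is broken.** It is not: envelopes stay sealed until the patient enters the study.
- **That preparation could be masked throughout at no cost.** It could be at the first treatment only. Later sessions would need a second person unaware of the arm, and even at the first treatment a device must be on hand.
- **That poor device fit will cause exclusions in the ambulatory arm alone.** Site suitability is an exclusion criterion for all patients and belongs before entry, and analysis is by intention to treat where possible. A fit problem first seen at application remains possible, but that justifies only confirming the criterion before opening.

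**Conclusion.** The point holds as a minor refinement. At the first treatment, a step common to both arms is done with knowledge of the arm when the order of steps does not require it. For that step, the general statement that the technician cannot be blinded is too broad.

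The scope is one treatment per patient. The size and direction of any bias are unknown from the documents, and a shift in the assumed range would be small beside a true 2 cm difference. The conclusion rests on two readings: that entry precedes preparation, and that the technician does the preparation. It does not show that the pain comparison as planned is biased. The case for change is that one avoidable route to performance bias can be removed from the first-treatment pain score at low cost.

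**What to change.** In Randomisation, replace the timing of envelope opening with wording such as:

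> At the first treatment the envelope will be opened only after written consent, baseline assessment, mapping and photography, confirmation that the site-suitability criterion is met, lesion scraping and application of MAL cream. It will be opened immediately before the dressing or device is applied.

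The ambulatory instruction that the device follows straight after the cream can still be met.

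Two small companions:
- Use varied block sizes if the list does not already. The technician opens every envelope, and with a known fixed block the last allocations could be deduced during preparation.
- Limit the Blinding statement to the steps after allocation, and say that preparation at day 7 and in any second cycle is done with the arm known.

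Cost: a short edit, and an Ambulight unit ready for every new patient, including those then allocated to conventional PDT. Since used units are posted back, cleaned, recharged and re-calibrated, availability needs planning. No extra staff, visits or patients are needed, and no sample-size or power figure changes.

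### Does the minimum of 36 rest on too small a standard deviation, so that recruiting 50 no longer covers drop-outs?

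*Combined protocol and SAP*

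**What the plan says.** The *Statistical power* paragraph of the combined protocol and SAP reports that mean pain with ambulatory treatment on the prototype device (12 patients) "was 1.25 (standard deviation 0.4) and was 5.26 (standard deviation 2.38) for a historical cohort" of 50 conventionally treated patients. It continues that "we estimated that to give 90% power" for means of 2 and 4 at the 5% level, "assuming two-sided testing, a minimum of 36 subjects would be needed". It then plans to "incorporate a safety margin recruiting 50 subjects given the old and frail nature of patients as this would account for any drop-outs". It gives no drop-out rate and does not name the standard deviations, test or allocation ratio behind the 36.

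*Results of pilot studies* describes the device that the trial will use. Eight patients with multiple lesions had a median pain score of 5.2 (range 2 to 9) cm on conventional treatment, "compared with 1.5 (0 - 3) cm for low irradiance Ambulight PDT". No standard deviation is given. *Data recording and analysis* commits only to "use of appropriate statistical tests comparing the pre-planned outcome measures".

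**The concern.** The ambulatory standard deviation of 0.4 comes from a prototype, and it is smaller than the Ambulight pilot range allows. A larger value raises the number needed, so the gap between 36 and 50 covers fewer losses than it appears to. Patients are described as old and frail, and the protocol says 50 accounts for any drop-outs.

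Recruitment adds to the worry. The protocol expects 60 to 80 new patients a year, 82% with a relevant diagnosis, and "we estimate that of these at least 50% should fit the eligibility criteria for the study". Over two years that is at least 2 × 60 × 0.82 × 0.5 = 49 to 2 × 80 × 0.82 × 0.5 = 66 eligible patients before refusals. If recruitment fell short, the sponsor might rely on 36 as sufficient when power at that number was below 90%.

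**Working it through.** **Inputs.** From *Statistical power*: difference 4 − 2 = 2, two-sided 5%, power 90%, SDs 0.4 and 2.38. From *Results of pilot studies*: eight patients, median 1.5, range 0 to 3. Assumptions: 1:1 allocation and one score per patient in the pilot.

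**Step 1: reproduce 36.** Take an unequal-variance (Welch) t test with n = 18 per arm.

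- Standard error = √[(0.4² + 2.38²)/18] = √(5.8244/18) = 0.569
- Noncentrality = 2/0.569 = 3.52
- Degrees of freedom = 17 × 5.8244²/(0.4⁴ + 2.38⁴) = 17 × 33.92/32.11 = 17.96
- Critical t = 2.10, so power = 91.3%

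At 17 per arm power is 89.6%. The smallest balanced total reaching 90% is therefore 36, as stated. With the same SDs, an equal-variance t test gives 34 and the normal approximation gives 32.

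**Step 2: what the Ambulight pilot allows.** For eight values with range 3 and median 1.5:

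- Smallest sample SD: one value at each end and six at 1.5, √(2 × 1.5²/7) = 0.80.
- Largest sample SD: four values at each end, √(8 × 1.5²/7) = 1.60.
- Central value if scores are roughly normal: the expected range of eight values is about 2.85 SDs, so 3/2.85 = 1.05.

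**Step 3: substitute**, keeping the conventional SD at 2.38.

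| Ambulatory SD | Total for 90% (Welch) | Losses allowed within 50 | Power at 36 | Power at 50 | Total for 90% (equal-variance t) |
|---|---|---|---|---|---|
| 0.40 | 36 | 14 | 91.3% | 97.8% | 34 |
| 0.80 | 38 | 12 | 89.6% | 97.1% | 36 |
| 1.05 | 40 | 10 | 87.8% | 96.2% | 38 |
| 1.60 | 46 | 4 | 81.6% | 92.6% | 46 |

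The losses column is 50 minus the Welch total.

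**Step 4: check the conventional SD.** The pilot's conventional range of 2 to 9 gives 7/2.85 = 2.46 by the same central method, close to 2.38. Using 1.05 and 2.46 together needs 42, still below 50.

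**Step 5: allowance in the planned difference.** The cited means differ by 5.26 − 1.25 = 4.01, and the pilot medians by 5.2 − 1.5 = 3.7. At the extreme ambulatory SD of 1.60, 36 patients give 90.8% power for a difference of 2.3 and 99% for a difference of 3.

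**The case for a change.** The case for amending the paragraph is that 0.4 cannot be squared with the pilot of the trial's own device. Sampling error does not explain it: if the true SD were 0.4 with normal scores, a sample SD of 0.80 from eight patients would give 7 × 0.643/0.16 = 28.1 on 7 degrees of freedom (0.643 = 4.5/7, the smallest sample variance), with probability about 0.0002. Nor does the mention of multiple lesions, since about 30 scores, nearly all at the mid-value, would be needed before 0.4 became possible. Under the method that reproduces 36, the minimum is too low at every SD the pilot permits. A reader must also guess the inputs, and two or three added sentences would cost nothing.

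Much of that is right. The paragraph is under-documented, and 36 is better read as about 40. Four things limit it.

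- The use of 0.4 is inferred, not stated. An equal-variance t test also returns 36 for ambulatory SDs of about 0.66 to 0.88, which includes the pilot's lower bound of 0.80.
- The margin of 14 is a subtraction. The protocol claims no such figure.
- The end of the range that would matter, 46 needed and 4 losses, requires four patients at exactly 0, four at exactly 3 and nobody near the reported median. At the other end the shortfall is one patient per arm.
- First-treatment pain is recorded seven days later, at the second-treatment visit. Only losses within that first week remove the score, so later drop-out in the one-year follow-up does not use up the margin for it.

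The recruitment figure of 49 to 66 is a floor built on an eligibility rate of at least 50%. It allows for a shortfall but does not show one.

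**Conclusion.** No change follows. The 36 is correct for the figures cited beside it. A more realistic ambulatory SD of about 1.05 would move the minimum to about 40 and the tolerable early losses within 50 to about 10. The number that governs the trial is 50, which gives about 96% power at that SD and at least 92.6% across the pilot's bounds if all 50 are evaluable. A rewritten paragraph would keep the same target, design and analysis, and would add only stated inputs and a sensitivity range. The missing test and SDs are a reporting gap that an analyst can fill sensibly when the results are written up.

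This rests on 1:1 allocation, one pilot score per patient, approximate normality and a conventional SD near 2.38. The 0.80 and 1.60 are bounds on a sample SD from eight patients, not a confidence interval for the true value. If the ambulatory arm varied as much as the conventional arm (SD 2.38 in both), 62 patients would be needed and 50 would give 83% power, but the pilot's maximum of 1.60 does not support so large a value. Taking the extreme bounds in both arms at once (conventional SD 1.87 to 3.74) gives totals from 26 to 90, which shows how little a pilot of eight can settle and is no ground for a different target.
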